### 4. Aims of the project

The study is a single-group 4-week trial of exploring the perceived efficiency and acceptability of remote real-time health monitoring system. The qualitative sub-study aims to explore the experience in setting up the remote health monitoring system, and the perceived benefits and acceptability of the care staff towards the system. The study deliverable will be a local testing protocol for future adaptation of remote health monitoring systems in elderly residential settings.

### 5. Outcomes

The primary outcomes include the efficiency of the system perceived by the care staff and staff perceptions on the whether the adoption of the system facilitates early detection of abnormal vital signs, facilitates early delivery of medical support, and reduces staff stress.

Ancillary outcomes include number of hospital admissions and any medical assistance due to the adoption of the system, and perceived benefits and acceptability of the care staff towards the system. The barriers and difficulties in the set-up of the system, and the concerns in choosing wireless or cable connection for the system are also explored.

## **6. Estimated duration and commencement data**

Project start date: March 2022

Testing period: March 2022 – April 2022

Proposed study completion date: April 2022

Expected final report date: June 2022

## **7. Scientific/historical background**

The vital signs of physically weak residents need to be continuously monitored so as to facilitate timely medical intervention. The procedures involved are labour intensive and time consuming. Moreover, during pandemic, a proportion of residents are infected with infectious disease, imposing threat to the staff who monitor their vital signs in close contacts. The application of remote monitoring system enables autonomous and continuous monitoring of vital signs without close contact between the residents and the staff. It is expected to reduce the time in monitoring the vital signs, however the efficiency is yet to be investigated. Apart from the potential time saving, the perceived benefits and acceptability of the stakeholders towards the system would also influence the future adoption of the system. Their perceived benefits and acceptability need to be explored.

Gerontechnology is playing a role in assisting the elderly in living independently, supporting their social interactions, improving their quality of life, and preventing emergencies. Conceptually, gerontechnology can be divided into four categories according to its use: first, gathering continuous data (e.g., heart rate and motion) to monitor the performance of older adults or detect falls through wearable sensors; second, assisting older people cognitively and socially using, for instance, interactive robotic pets; third, providing care or monitoring of health from a distance, with the help of telecare or telemedicine; and finally, compensating for possible technology deficits in the home environment, which mainly refers to a smart home. In this study, gerontechnology is used as an umbrella term for all the aforementioned technologies. Gerontechnology helps older adults maintain their

health and wellbeing in their homes, which is considered to be of positive significance to aging in place. Using telecommunications, gerontechnology can now provide health professionals and caregivers with remote access to older patients. In addition, gerontechnology has shown great potential in reducing escalating medical costs by eliminating the need for expensive and limited medical facilities. In the context of the accelerated aging process, gerontechnology already has a broad market prospect, and delivering healthcare services based on gerontechnology has been one of the trends of providing care for older adults in Hong Kong.

Compared to developed countries, the smart health technology of China is still in its infancy. It was only in 2020 that the Social Innovation and Entrepreneurship Development Fund and other NGOs first introduced the Gerontechnology Platform specifically work on projects on improving access and evaluating technology-based applications and innovations for consumer (elderly use at home) and healthcare settings (e.g., elderly home and geriatric hospital ward setting). Thus, although several international studies have explored the perspectives of the care staff in residential homes and healthcare settings on emerging technologies across the world, the data on Hong Kong are still insufficient. Thus, this study aims to determine:

1. The intention of the care staff in residential homes and community isolation facility in Hong Kong to adopt gerontechnology.
2. The factors influencing the adoption intention and use of gerontechnology.

Gerontechnology, based on the elderly users' needs, is playing a role in improving the daily functions of the elderly. Piau et al. (2014) mentioned that gerontechnology can help the elderly in living independently and support their social interactions. They classified gerontechnology applications by the elderly users' needs: social isolation (e.g., mobile phone technologies and social media apps), functional decline (e.g., robotic vacuums and electric wheelchairs), and cognitive disorders and Behavioral and Psychological Symptoms of Dementia (BPSD) (e.g., telemonitoring and location tracking technologies). Carmeli (2009) indicated that gerontechnology such as "smart or future homes" allows the elderly to control their environments, and therefore they improve their overall quality of life, increase independence,

and prevent emergencies. This study refers to the abovementioned gerontechnology application contexts and then explains the products and services of gerontechnology for the participants by giving some examples, such as “mobile phones for the elderly, social media apps, robotic vacuums, electric wheelchairs, wearable healthcare monitoring systems, location tracking technologies, and smart homes”. The study will be conducted in compliance with the protocol, GCP and the applicable regulatory requirement(s).

## **8. Research Questions**

The study has 3 primary research questions and 6 secondary research questions targeting care staff in the setting of residential homes for the elderly and community isolation facilities. The 3 primary research questions are:

- (1) Will care staff perceive the remote real-time health monitoring system as efficient?
- (2) Will the system facilitate any early detection of abnormal vital signs?
- (3) Will the system facilitate early delivery of medical support?

The 6 secondary research questions are:

- (4) What are the numbers of hospital admissions and further medical assistance due to the adoption of the system?
- (5) Will the system reduce the stress level of the care staff?
- (6) What are the perceived benefits and acceptability of the care staff towards the system?
- (7) What should be considered when developing the evaluation framework for the adaption of the system in elderly residential setting?
- (8) Are there any barriers and difficulties in the set-up of the system?
- (9) What are the concerns in choosing wireless or cable connection for the monitoring device?

## **9. Study design**

This is a single-group 4-week trial of using the remote health monitoring system. All care staff who manage the system will complete a very brief survey (1-minute) after each work shift for 2 weeks. Detection of abnormal vital signs will be recorded by the system. Hospital admission and further medical assistance due to the adoption of the system will be counted by the care team. The care staff will be interviewed about the set-up of the system, their perceived benefits and acceptability of the system.

## **10. Subjects**

Care staff in study sites who are responsible to set up and operate real-time remote health monitoring system will be recruited. They also need to be able to read and understand Chinese.

## **11. Procedures**

### **11.1 Implementation**

The remote monitoring system will constantly record the temperature, pulse and SpO2 of the residents wearing the equipment. When the staff find abnormal vital signs, they will provide further medical assistance. After every shift during the trial period for 2 weeks, they will fill in a 1-minute survey.

### **11.2 Data collection**

The remote monitoring system will remotely and real-time record the temperature, pulse and SpO2 of the residents wearing the sensor. When the staff are notified of any abnormal vital signs by the system via screen display and notification sound, they will deliver further medical assistance. Hospital admission and further medical assistance due to the adoption of the system will be counted by the care team under pre-existing practice. After every shift during the trial period for 2 weeks, the staff will fill in a 1-minute survey about their operation and perceived efficiency of the system, such as facilitating more frequent monitoring of particular residents' vital signs, the provision of further medical assistance, perceived time saving in monitoring vital signs, and acceptability of the system. They could record their experience of using the system in written format or in a mobile phone messaging app (such as Whatsapp) in audio format. If they fill in the survey for fewer than 8 times during the 2 weeks, they would be invited to continue to fill in the survey after work shift for an extra week until they fill in it for at least 8 times. Meanwhile, as a staff

may complete more than 1 shift per day, they would not be invited to fill in the survey after having completed it for 12 times. At the end of the trial, HOHCS staff will provide the number of abnormal vital signs recorded by the system, number of hospital admissions and further medical assistance without any personal identifiers to HKU research team. All data collected that is related to residents is not identifiable.

There are two parts of the qualitative sub-study. When the system is set up, the unit IC and care staff responsible to set up the system from each participating unit will be interviewed by HKU research assistant(s). Themes of qualitative questions include: (1) barriers and difficulties in the set-up of the system; and (2) the concerns in choosing wireless or cable connection for the monitoring device. Meanwhile, when the main trial ends, a total of 9-15 care staff from all participating units responsible to operate the system will be interviewed about their perceived benefits and acceptability of the system. Themes of qualitative questions include: (1) Acceptance of using the remote health monitoring system (including ease of operation, care staff's confidence and convenience in using the system); (2) Benefits of using the remote health monitoring system (including usefulness of the innovation, impacts on quality of care); (3) Concerns in using the remote health monitoring system (including if any residents stop using the sensor and the reason behind); and (4) Overall perception of using the remote health monitoring system. For both parts of the qualitative sub-study, an interview guide with open-ended and iterative questions will be used to probe for more experiences from the interviewees. Each interview will be conducted by a trained research assistant and will last about 15 - 30 minutes.

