## **14. Data analyses**

The proportion of all the responses in the staff survey will be calculated. The numbers of abnormal vital signs, hospital admission and further medical assistance due to the adoption of the system will be counted.

The qualitative interview content will be transcribed verbatim in Chinese for further analysis. The qualitative interview transcripts will be analyzed using framework analysis to construct a coherent and logical structure from the classification of many opinions and perceptions of the system. The results will then be discussed and consolidated in the panel meetings with the co-authors.

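### Does the missing start day of the 2-week staff survey within the 4-week trial call for a change to the plan?

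*Combined protocol and SAP*

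**What the plan says.** Section 9 sets the length of the study: "This is a single-group 4-week trial of using the remote health monitoring system". The survey is shorter. Section 11.1 says "After every shift during the trial period for 2 weeks, they will fill in a 1-minute survey", and Section 11.2 repeats this almost word for word: "After every shift during the trial period for 2 weeks, the staff will fill in a 1-minute survey".

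Section 11.2 then adds two limits for each staff member. Those below 8 completions after the 2 weeks are asked to carry on "for an extra week until they fill in it for at least 8 times". At the upper end, "they would not be invited to fill in the survey after having completed it for 12 times".

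Other data are tied to the end of the trial. For the event data, "At the end of the trial, HOHCS staff will provide the number of abnormal vital signs recorded by the system", together with the admissions and assistance counts. For the second part of the qualitative sub-study, staff are interviewed "when the main trial ends, a total of 9-15 care staff from all participating units".

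Section 14 gives the survey analysis in one sentence: "The proportion of all the responses in the staff survey will be calculated". Sections 6 and 16 give the calendar in months only. No section says on which day after go-live the survey opens, whether all units open it together, or whether the extra week must end within the 4 weeks.

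**The concern.** The survey carries perceived efficiency, which Section 5 lists among the primary outcomes and Section 8 makes the first research question. Staff opinion of a new device may differ between the first days of use and a period when it is routine. If the survey can fall anywhere in the 4 weeks, a reader of the final proportions cannot tell from the plan which phase of use they describe.

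The length of follow-up also varies by person. A staff member stops at the 12th survey, at the end of survey week 2, or during the extra week. Section 14 pools every response without reference to survey week. With a late enough start, some catch-up surveys would be completed after the trial had closed, and possibly after the same person had been interviewed on much the same topics.

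**Working it through.** The plan gives no survey start or end day, so there is no figure of its own to reproduce. The check is calendar arithmetic.

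**Inputs from the plan**
- Trial length: 4 weeks = 28 days (Section 9), numbered 1 to 28.
- Main survey window: 2 weeks = 14 days (Sections 9, 11.1 and 11.2).
- Catch-up: 7 further days for staff below 8 completions (Section 11.2). Staff are said to continue, so it is taken to follow directly.
- Staff: 12 to 20 (Section 13).

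**Where the windows fall.** Let the survey open on trial day S.
- The main window ends on day S + 13. It lies inside the trial if S + 13 ≤ 28, so S ≤ 15.
- The catch-up week ends on day S + 20. It lies inside the trial if S + 20 ≤ 28, so S ≤ 8.

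| Survey opens (S) | Main window ends | Catch-up ends | Days past day 28 |
|---|---|---|---|
| 1 | 14 | 21 | 0 |
| 8 | 21 | 28 | 0 |
| 9 | 22 | 29 | 1 |
| 15 | 28 | 35 | 7 |

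If the first day is counted as day 0, the same limit reads as day 7 instead of day 8.

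**What share of the trial is surveyed.** The main window covers 14/28 = 50% of the trial days. With catch-up the figure is at most 21/28 = 75%.

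**Who could be affected by an overrun.** Only staff below 8 completions on survey day 14. The plan gives no rosters, so the following are assumptions, with a survey completed after every shift.
- Four shifts a week gives 4 × 2 = 8 by survey day 14, so there is no catch-up.
- Three shifts a week gives 3 × 2 = 6 by survey day 14, so 8 − 6 = 2 surveys remain. The 8th falls between survey day 16 (shifts on the first three days of each week) and survey day 20 (shifts on the last three).
- Under the latest start, S = 15, those 2 of 8 responses (25%) for that person would come after day 28. Under a start at go-live, S = 1, they come on or before trial day 20.

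**What the analysis does with the responses.** Section 14 calculates proportions and counts. It plans no test, no comparison between periods and no model over time, and none of the nine research questions in Section 8 asks about change across the 4 weeks. Changing S alters which days the proportions describe. It does not alter how they are calculated, and there is no contrast for it to bias.

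**The case for a change.** The best argument for a change is that the study's deliverable, in Section 4, is a local testing protocol for others to adapt. A testing protocol that does not say when the survey opens cannot be repeated exactly as it was run. The remedy would be a sentence or two, with no extra surveys or staff. A table by survey week could also show that week 3 comes only from staff who were below 8 completions, and that the cap of 12 can remove staff on two shifts a day as early as survey day 6 (12/2 = 6).

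Part of this stands. The start day is indeed unstated, and the phrase about 2 weeks during the trial period is loose enough that it could be misread as a 2-week trial. A report that did not give the survey dates would be less useful.

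The rest carries little weight. The final report can give the actual survey dates, and that serves a later user better than a planned day would. No choice of start is clearly superior: opening at go-live leaves week 4 unsurveyed, while opening in week 2 leaves week 1 unsurveyed. Later experience is also picked up by the interviews at the end of the trial, which cover acceptance, benefits, concerns and overall perception. A table by week would be thin with 12 to 20 staff, its last row might hold very few people, and it would answer no question that the plan asks.

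**Conclusion.** No change to the plan is needed. The start day is a missing detail, and the ordinary reading fills it: staff complete the survey after shifts on which they operate the system, so it opens when they begin to use it. On that reading everything ends by day 21 of 28. The plan's own figures are compatible for every start up to day 8. An overrun of 1 to 7 days needs a late start that nothing in the plan suggests, and it would touch only the few surveys that staff below 8 completions still owed.

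This rests on three assumptions: the extra week follows the 2 weeks without a break, trial days are numbered from 1, and the opening pages that were not available for review do not set a different schedule. The 4-week length and the 8 and 12 limits come from the plan; the rosters used above do not, and the conclusion does not depend on them. Confidence is high on the arithmetic and on the absence of a start day in the available text. What remains is a matter for reporting: the proportions describe the survey window and should not be presented as covering all 4 weeks.

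### If the early-detection and early-support items are answered per shift, the planned all-response proportions mix how often residents were abnormal with how helpful the system was judged

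*Combined protocol and SAP*

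**What the plan says.** Sections 9, 11.1 and 11.2 all tie the survey to the shift and not to an event. Section 9 has it as: "All care staff who manage the system will complete a very brief survey (1-minute) after each work shift for 2 weeks". Section 11.2 repeats the rule ("After every shift during the trial period for 2 weeks, the staff will fill in a 1-minute survey"), aims for at least 8 surveys per person (with an extra week if needed) and stops inviting a person after 12.

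Section 5 makes staff perception the primary outcome, including whether the system "facilitates early detection of abnormal vital signs, facilitates early delivery of medical support". Questions 2 and 3 of the three primary research questions in section 8 cover the same two subjects.

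Section 11.2 makes assistance follow an abnormal sign: "When the staff are notified of any abnormal vital signs by the system via screen display and notification sound, they will deliver further medical assistance". Its open list of survey topics includes "the provision of further medical assistance, perceived time saving in monitoring vital signs, and acceptability of the system". Early detection is not named in that list.

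The survey analysis in section 14 is one sentence: "The proportion of all the responses in the staff survey will be calculated". The data on abnormal signs come separately and as totals. At the end of the trial "HOHCS staff will provide the number of abnormal vital signs recorded by the system", together with the numbers of admissions and assistance.

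**The concern.** Early detection and early support can be observed only in a shift when some resident's vital signs became abnormal. In a quiet shift there is nothing to detect and no support to bring forward. The survey is completed after quiet shifts too, and section 14 names no denominator other than all responses.

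If the items ask about the shift just worked, a respondent after a quiet shift has no natural answer. Whatever is ticked goes into the proportion. The result then depends on three things: how often residents were abnormal, how helpful the system was when they were, and how staff chose to answer when the question did not apply. Only the second is the outcome of interest.

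The plan as described cannot separate them afterwards. Abnormal signs and assistance arrive as totals, and no link to a shift or a survey is described. Unless the information is collected with each survey, the analysis cannot recover it.

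**Working it through.** The plan gives no power, effect size or calculated sample size (section 13 bases the 12-20 staff on availability), so there is no figure to reproduce. The check is arithmetic on the proportion that section 14 plans.

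**Inputs from the documents**
- Staff: 12 to 20 (section 13).
- Surveys per person: target of at least 8, at most 12 (section 11.2).

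**Inputs that the documents do not give (assumed)**
- q, the share of surveyed shifts with an abnormal sign: 0.1 to 1.0.
- h, the share of those shifts in which the system is judged helpful: 0.9 or 0.5.
- r, the share of event-free shifts answered 'yes': 0 and 1 are the two extremes.

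**Number of surveys.** 12 × 8 = 96 to 20 × 12 = 240, if everyone reaches the target of 8.

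**All-shift proportion of 'yes'.** P = q × h + (1 − q) × r. At r = 0 this is q × h. At r = 1 it is q × h + (1 − q). The gap between the extremes is 1 − q.

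| q | h = 0.9, r = 0 | h = 0.9, r = 1 | h = 0.5, r = 0 | h = 0.5, r = 1 |
|---|---|---|---|---|
| 0.1 | 9% | 99% | 5% | 95% |
| 0.3 | 27% | 97% | 15% | 85% |
| 0.5 | 45% | 95% | 25% | 75% |
| 0.8 | 72% | 92% | 40% | 60% |
| 1.0 | 90% | 90% | 50% | 50% |

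For example, at q = 0.1 and h = 0.9: 0.1 × 0.9 = 0.09, and 0.09 + 0.9 = 0.99.

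**One result, two explanations.** With r = 0, an observed 27% arises from h = 0.9 and q = 0.30 (0.30 × 0.9 = 0.27). It also arises from h = 0.5 and q = 0.54 (0.54 × 0.5 = 0.27). The proportion alone cannot tell these apart.

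**Restricted to shifts with an abnormal sign.** The proportion equals h whatever q and r are. The denominator becomes q times the number of surveys:
- q = 0.1: 9.6 to 24
- q = 0.3: 28.8 to 72
- q = 0.5: 48 to 120

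**The case against.** **The instrument is not visible.** The form is not in the available text, and the timeline in section 16 lists it as still to be prepared. Wording, answer options and recall period are unknown, and early detection is not named as a survey topic in section 11.2. A form with a 'not applicable' answer would reduce the problem. This stands, and it is why the point is conditional. Even with such an answer, section 14 does not say how it would be handled.

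**The outcome may be a general opinion.** Section 5 speaks of perceptions of whether adopting the system helps, and staff can hold such a view after any shift. If quiet shifts are answered from that view, r is close to h, P is close to h, and the distortion largely disappears. This is a fair reading, but the plan does not choose it.

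**The denominator is one reading.** Section 14 could mean the frequency of every answer option, including any 'not applicable'. That is possible, but not stated.

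**Other data bear on the same questions.** The system counts, staff comments and end-of-trial interviews give context. They do not correct the survey proportions.

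**Stronger readings.** A reader might infer that units with stable residents will make the system look unhelpful. The documents do not support this: r = 1 moves the result the other way, and section 14 plans no comparison between units. A reader might also infer that staff would have to answer 'no' after a quiet shift, or that primary questions 2 and 3 measure only case mix. The first needs a form that is not available. The second ignores the general-opinion reading and the separately collected counts.

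**Conclusion.** The point holds in conditional form. If the two items are answered per shift, the planned proportions mix event frequency with judged helpfulness, and the data as described give no way to separate them. The possible size is large when events are rare and nil when every shift has one: 9% or 99% at q = 0.1, and 90% either way at q = 1.0, all with h = 0.9. The values of q, h and r are assumptions, and the direction of any distortion is unknown.

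Two primary perception outcomes are affected. The study is small, single-group and descriptive, with no hypothesis test planned, so what is at risk is the interpretation of two reported proportions. The change is still worth making before data collection, because the missing information has to be recorded shift by shift.

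**What to change.** **Survey.** Add one item to each form: did any resident have an abnormal vital sign in this shift (none / alerted by the system / found by staff without a system alert)? Add a 'not applicable' answer to the early-detection and early-support items.

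**Section 14.** Report both proportions among shifts with any abnormal sign, whether or not the system alerted and whether or not assistance followed. Give the number of such shifts and show the all-shift proportion alongside. Keep the all-shift denominator for efficiency, time saving and acceptability.

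The denominator should not be narrower than this. Counting only shifts with a system alert would drop the abnormal signs that the system missed. Counting only shifts with both an alert and assistance would condition on part of the outcome. Both choices would favour the system. An abnormal sign that nobody noticed stays out of reach either way.

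**Cost.** One extra tick-box in a 1-minute survey, a 'not applicable' answer on two items, a short addition to section 14, and a smaller denominator for those two items: about 29 to 72 of 96 to 240 surveys at an assumed 30% event rate.

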## **13. Sample size determination**

The sample size is estimated by the number and availability of the staff in the participating units. It is estimated that a total of 12-20 staff will be recruited.

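### The totals of abnormal vital signs, medical assistance and hospital admissions have no planned denominator: residents fitted, time worn and residents who stopped are not recorded

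*Combined protocol and SAP*

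**What the plan says.** - **Source of the signals.** Under Section 11.1 the system will "constantly record the temperature, pulse and SpO2 of the residents wearing the equipment". Section 11.2 likewise ties the recording to residents with a sensor on.
- **What is handed over.** Section 11.2 describes one closing transfer, free of identifiers: "HOHCS staff will provide the number of abnormal vital signs recorded by the system, number of hospital admissions and further medical assistance".
- **What is done with it.** Section 14: "The numbers of abnormal vital signs, hospital admission and further medical assistance due to the adoption of the system will be counted". No rate is mentioned.
- **Stopping.** This appears once, inside the third interview theme in Section 11.2 (concerns about the system): "including if any residents stop using the sensor and the reason behind". The interviews take place when the main trial has ended, and "a total of 9-15 care staff from all participating units responsible to operate the system will be interviewed".
- **Numbers and duration.** Section 9: "This is a single-group 4-week trial of using the remote health monitoring system". Section 13: "It is estimated that a total of 12-20 staff will be recruited". No number of residents is given anywhere.
- **Use of the results.** The second primary question in Section 8 asks about early detection of abnormal vital signs. The fourth question asks for the numbers of admissions and episodes of assistance. Section 4 names the deliverable as a testing protocol for later use in elderly residential settings.

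**The concern.** An alert can occur only while a sensor is worn, so the alert total is the product of an event frequency and an amount of worn time. The plan collects the total and not the worn time. It also omits the number of residents fitted, so worn time cannot even be approximated.

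Two uses are affected. First, the alert total is the only system-recorded figure bearing on the second primary question. Without a denominator, a small total may reflect stable residents, a small number fitted or sensors left off, and these readings cannot be separated. Second, the study runs in several units and is meant to feed a testing protocol for other homes. Raw totals from units of unknown size and unknown wear cannot be set against each other or scaled to a home of another size.

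**Working it through.** **Is a denominator planned anywhere?** The relevant sections, side by side:

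| Section | Residents fitted | Residents who stopped | Time worn |
|---|---|---|---|
| 5 Outcomes, 8 Research questions | no | no | no |
| 11.2 End-of-trial transfer | no | no | no |
| 11.2 Shift survey (topics listed) | no | no | no |
| 11.2 Closing interviews | no | asked about, no count planned | no |
| 13 Sample size | no (staff only) | no | no |
| 14 Data analyses | no | no | no |

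**The plan's own figure.** The only sample figure is 12-20 staff. It rests on availability, so there is no formula to reproduce, and it says nothing about residents.

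**Illustration. All inputs except the duration are assumed.**
- Duration: 28 days (4 weeks, Section 9).
- Alerts: A = 20 (assumed).
- Residents fitted: N = 10, 20 or 40 (assumed).
- Proportion who stop: f = 0, 10%, 25% or 50% (assumed).
- Sensor-days: N × 28 × (1 − f/2) if stopping falls at mid-trial on average, or N × 28 × (1 − f) if it falls at the start.
- Rate per 100 sensor-days = 100 × A / sensor-days.

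*Step 1: nobody stops, only N is unknown.*
- N = 10: 280 sensor-days, 2000/280 = 7.14
- N = 20: 560 sensor-days, 2000/560 = 3.57
- N = 40: 1120 sensor-days, 2000/1120 = 1.79

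This is a fourfold spread with no stopping at all.

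*Step 2: N fixed at 20, only stopping is unknown.*

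| f | Mid-trial: sensor-days, rate | At start: sensor-days, rate |
|---|---|---|
| 10% | 532, 3.76 | 504, 3.97 |
| 25% | 490, 4.08 | 420, 4.76 |
| 50% | 420, 4.76 | 280, 7.14 |

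Against 3.57 with no stopping, the rate rises by a factor of 1.05 (560/532) to 2.0 (560/280).

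*Step 3: an intermediate case.* With 30 residents there are 30 × 28 = 840 sensor-days and a rate of 2.38.
- If 30% stop at day 7: 21 × 28 + 9 × 7 = 651 sensor-days, rate 3.07.
- If 50% stop at day 7: 15 × 28 + 15 × 7 = 525 sensor-days, rate 3.81, which is 60% higher (840/525 = 1.6) for the same 20 alerts.

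*Step 4: both unknown.* The lowest rate is 2000/1120 = 1.79 (40 residents, none stop). The highest is 2000/140 = 14.29 (10 residents, half stop at the start). The ratio is 8, made up of a factor of 4 from the number of residents and 2 from stopping.

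The ratios do not depend on the assumed 20 alerts, which cancel.

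**The case against.** The strongest reply is that this is a small descriptive study of staff. The primary outcomes in Section 5 are staff perceptions, which need no wear-time denominator. The fourth research question asks for numbers, and a count answers it. No rate, control group, test or comparison between units is planned. All of this stands, and it limits the point to the reading of the alert total and the usefulness of the three totals outside the units that produced them.

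The text may also tempt a reader into stronger claims that it does not support:

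- **That unrecorded stopping is what removes the denominator.** It would be missing even if every resident wore the sensor throughout, because the number fitted is not recorded. In the illustration that number matters more than stopping.
- **That a measure of acceptability in the plan is lost.** The aim in Section 4 speaks broadly of "exploring the perceived efficiency and acceptability of remote real-time health monitoring system", but the outcome in Section 5 and the sixth research question concern acceptability to care staff, which the survey and interviews do measure. Sensor removal would tell us about residents, whose acceptance is not a listed outcome.
- **That stopping can surface only through recall at interview.** Staff may also record their experience in writing or by audio message during the trial. The survey topics are given as examples, and the form is not shown. None of these routes is planned to give a count, but they rule out saying that interviews are the only source.
- **That frailer or acutely ill residents stop more often, so that events are understated in them.** This is plausible, but no section says so, and the denominator problem does not need it.
- **That the system already holds worn time ready for use.** The documents say that it records temperature, pulse and SpO2 of wearers. They do not say that resident-days can be extracted from it.

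**Conclusion.** The point holds in a limited form. If the plan is followed exactly, the three totals arrive without residents fitted, number stopped or time worn. They remain valid as counts and answer the fourth research question. They cannot be turned into rates, compared between units or scaled for the testing protocol, and the alert total cannot separate few events from few residents or little wear.

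The size cannot be derived from the documents. On the assumed ranges, one and the same total is compatible with an eightfold range of rates, most of it due to the unstated number of residents. With stopping as low as 10% at mid-trial, stopping alone moves the rate by only about 5%.

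It would go too far to infer that the totals are meaningless or that the primary outcomes are compromised, since those outcomes are staff perceptions. Nor would a denominator make the alert total evidence of *early* detection in a single-group study; it would only make the frequency readable. This is a worthwhile and inexpensive improvement, not a defect that invalidates the study.

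**What to change.** **Section 11.2.** Add three figures to the end-of-trial transfer, per unit and without identifiers:
1. number of residents fitted with a sensor;
2. number who stopped before the end of the trial;
3. total sensor-days, from the system log if it can be extracted, otherwise from fitting and stopping dates.

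All three are needed, because a count of those who stopped does not by itself give worn time.

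**Section 14.** Report abnormal vital signs, further medical assistance and hospital admissions both as counts and per 100 sensor-days. Report the proportion of fitted residents who stopped as a descriptive feasibility figure, not as a staff acceptability outcome. Leave the reasons for stopping to the interviews, which suit that purpose.

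**Cost.** A small tally by the staff who already supply the totals. If the log cannot be used, fitting and stopping dates must be noted as the trial runs, so this should be settled before it starts. Unit totals fit the rule in Section 11.2 that resident data are not identifiable, and recruitment and interviews do not change. Two limits should be stated in the report: gaps in the signal may reflect device faults as well as removal (Section 15 anticipates damage and repair), and sensor-days taken from dates will miss short removals.
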